6.1.2.2 Pediatrix Administrative Database Review

Data will be extracted from the Pediatrix Medical Group Database. The following clinical and demographic variables will be included in addition to date of birth, gestation age, race, ethnicity, sex, and birth weight (Table 3).

Table 3: Variables Collected for Pediatrix Safety Study

	Date of birth	-3 days	-2 days	-1 day	On ampicillin	+1 day	+2 days	+3 days
Adverse Events (new onset)								
Cardiorespiratory arrest					X			
Hypotension					X			
Tachypnea					X			
Tachycardia					X			
Medical NEC					X			
Surgical NEC					X			
Focal intestinal perforation					X			
Grade II IVH					X			
Grade III or IV IVH					X			
Periventricular leukomalacia					X			
Cystic periventricular leukomalacia					X			
PDA requiring medical treatment					X			
PDA requiring surgical treatment					X			
Rash					X			
Seizure					X			
ROP requiring laser surgery					X			
Hyperbilirubinemia requiring exchange transfusion					X			
Laboratory Values								
AST		X	X	X	X	X	X	X
ALT		X	X	X	X	X	X	X
GGT		X	X	X	X	X	X	X
Direct bilirubin		X	X	X	X	X	X	X
WBC count		X	X	X	X	X	X	X
Neutrophil count		X	X	X	X	X	X	X
Hematocrit		X	X	X	X	X	X	X
Platelets		X	X	X	X	X	X	X
BUN		X	X	X	X	X	X	X
Creatinine		X	X	X	X	X	X	X
Glucose		X	X	X	X	X	X	X
Sodium		X	X	X	X	X	X	X
Potassium		X	X	X	X	X	X	X
Calcium		X	X	X	X	X	X	X
Magnesium		X	X	X	X	X	X	X
Phosphorus		X	X	X	X	X	X	X
Base excess		X	X	X	X	X	X	X
Positive Blood/Urine/CSF Cultures								
Organism		X	X	X	X	X	X	X
Ampicillin Dosing								
Days of administration					X			
Clinical Variables								
Mechanical ventilation					X			
Fraction of inspired oxygen					X			
Concomitant medications					X			

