10.4.2 Objective #2

Severity of diagnoses and laboratory values will be assigned according to predetermined definitions (see Appendix tables 4 and 5). A diagnosis (Appendix table 4) will be attributed to ampicillin if it was first made on a day that the infant was exposed to ampicillin. A laboratory abnormality (Appendix table 5) will be attributed to ampicillin if it occurred on a day that the infant was exposed to ampicillin or one day after exposure to ampicillin. For the cohort of patients from the PPRU Antimicrobial PK in High Risk Infants study enrolled at Reda, the frequency of diagnoses and laboratory abnormalities attributed to ampicillin will be described using standard summary statistics. For the patients exposed to ampicillin in the Pediatrix database, the frequency of diagnoses and laboratory abnormalities attributed to ampicillin will be compared to those not attributed to ampicillin. Multivariable logistic regression analyses will be performed to evaluate the association between diagnoses and laboratory abnormalities and ampicillin controlling for clinical factors associated with poor outcome in infants such as mechanical ventilation, inotropic support, and demographic features including race, gender, gestational and postnatal age. Outlier diagnostics and evaluation for multicollinearity will be performed using standard techniques. The full model containing all clinically relevant variables listed above will be compared to scaled down models using likelihood ratio tests, and the most parsimonious model that fits the data will be used for analysis. The odds of a diagnosis or laboratory abnormality occurring on a day the infant was exposed to ampicillin will be compared to the odds of occurrence on a day the infant was not exposed to ampicillin. Odds ratios and 95% confidence intervals derived from this model will be reported.

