19 APPENDIX

Table 4. Diagnoses

Body System	Diagnoses	Serious Diagnoses
Gastrointestinal	Medical NEC	Surgical NEC
		Focal intestinal perforation
Neurologic	Grade II IVH	Grade III or IV IVH
	Periventricular leukomalacia	Cystic periventricular leukomalacia
		Seizure
Cardiovascular	PDA requiring medical treatment	PDA requiring surgical treatment
	Hypotension requiring pressors	Cardiorespiratory arrest
	Tachycardia	
Ophthalmology		ROP requiring laser surgery
Hematology		Hyperbilirubinemia requiring exchange transfusion
Dermatology	Rash	
Respiratory	Tachypnea	

IVH=intraventricular hemorrhage
 PDA=patent ductus arteriosus

NEC=necrotizing enterocolitis
 ROP=retinopathy of prematurity

Table 5. Laboratory Values

Laboratory Values	Abnormality	Serious Abnormality
Serum Electrolytes		
Hypoglycemia	< 40 mg/dL	< 20 mg/dL
Hyperglycemia	> 250 mg/dL	> 400 mg/dL
Hyponatremia	< 125 mmol/L	< 115 mmol/L
Hypernatremia	> 150 mmol/L	> 160 mmol/L
Hyperkalemia	> 6 mmol/L	> 7.5 mmol/L
Hypokalemia	< 3 mmol/L	< 2.5 mmol/L
Hypercalcemia (iCa)	> 12.5 mg/dL (>1.5 mmol/L)	> 13.5 mg/dL (>1.6 mmol/L)
Hypocalcemia (iCa)	< 6.0 mg/dL (<0.9 mmol/L)	< 5.0 mg/dL (< 0.8 mmol/L)
Hypermagnesemia	> 3.5 mg/dL	> 4.5 mg/dL
Hypomagnesemia	< 1.5 mg/dL	< 1.2 mg/dL
Hyperphosphatemia	> 9.5 mg/dL	> 10.5 mg/dL
Hypophosphatemia	< 3.5 mg/dL	< 2.5 mg/dL
Base Excess	< -10 mmol/L	< -15 mmol/L
Renal Dysfunction		
Elevated BUN	> 70 mg/dL	> 100 mg/dL
Elevated Creatinine	> 1.7 mg/dL	> 3.0 mg/dL
Liver Dysfunction		
Elevated AST	> 5 x upper limit of normal	> 10 x upper limit of normal
Elevated ALT	> 5 x upper limit of normal	> 10 x upper limit of normal
Elevated GGT	> 5 x upper limit of normal	> 10 x upper limit of normal
Direct bilirubin	> 5 mg/dL	>10 mg/dL
Complete Blood Count		
Leukocytosis	> 25,000/mm ³	> 40,000/mm ³
Leukopenia	< 5000/mm ³	< 2000/mm ³
Neutropenia	< 500/mm ³	< 100/mm ³
Thrombocytopenia	< 100/mm ³	< 30/mm ³
Thrombocytosis	> 600,000/mm ³	> 1,000,000/mm ³

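### The hypotension model adjusts for inotropic support, which overlaps the outcome's own definition, and the protocol does not fix when that support is measured

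*Protocol*

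**What the plan says.** Section 10.4.2 describes a single modelling approach for all safety outcomes: "Multivariable logistic regression analyses will be performed to evaluate the association between diagnoses and laboratory abnormalities and ampicillin". The adjustment set is named once, for all of these models together: they are fitted "controlling for clinical factors associated with poor outcome in infants such as mechanical ventilation, inotropic support", plus race, gender, gestational age and postnatal age. The full model is said to hold every clinically relevant variable in that list. It is then reduced by likelihood ratio tests, and "the most parsimonious model that fits the data will be used for analysis". No outcome has its own covariate list.

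The outcomes come from the appendix: "Severity of diagnoses and laboratory values will be assigned according to predetermined definitions (see Appendix tables 4 and 5"). Among the 17 diagnoses in Table 4, the cardiovascular group includes "Hypotension requiring pressors".

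The unit of comparison is the infant-day: "The odds of a diagnosis or laboratory abnormality occurring on a day the infant was exposed to ampicillin" is set against the odds on an unexposed day. A diagnosis is attributed to ampicillin "if it was first made on a day that the infant was exposed to ampicillin".

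Table 3 (section 6.1.2.2) has no inotrope row; the nearest is concomitant medications. That row and mechanical ventilation are marked only in the on-ampicillin column, the same column as the adverse events. Laboratory values, by contrast, are marked from three days before to three days after. The event row in Table 3 reads "Hypotension X", without the pressor requirement, and Table 2 uses the same short label.

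**The concern.** A covariate should describe the infant's state before the outcome or independently of it. Here an infant-day becomes a hypotension event only if pressors were needed, and the model then adjusts for a class of treatment that includes much of the same drug use. If that treatment is recorded on the event day, the model conditions on part of the outcome. Nearly all the information on ampicillin then comes from days on inotropes. The question becomes whether, among those days, new hypotension is more common with ampicillin, rather than whether ampicillin days carry more new hypotension.

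At stake is one of the cardiovascular safety estimates. A real signal could be hidden, or an apparent one created, depending on how often inotropes run for other reasons on exposed and unexposed days.

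**Working it through.** The protocol gives no event rate, effect size or power for this outcome, so there is no figure of its own to reproduce. All rates below are assumptions.

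**Set-up.** Let p0 and p1 be the event probability on unexposed and exposed days. Let o0 and o1 be the share of non-event days with an inotrope on unexposed and exposed days. Let s be the share of event days on which an inotrope is recorded. The true odds ratio is OR = [p1/(1 − p1)] / [p0/(1 − p0)].

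**Every event day carries an inotrope (s = 1).** Days without an inotrope contain no events and say nothing about ampicillin. Within inotrope days the odds of an event are p1/[(1 − p1)·o1] when exposed and p0/[(1 − p0)·o0] when unexposed. The ratio is

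adjusted OR = OR × o0/o1.

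| o0 | o1 | o0/o1 | True OR 1 becomes | True OR 2 becomes |
|---|---|---|---|---|
| 2% | 2% | 1.00 | 1.0 | 2.0 |
| 2% | 4% | 0.50 | 0.5 | 1.0 |
| 2% | 6% | 0.33 | 0.33 | 0.67 |
| 4% | 2% | 2.00 | 2.0 | 4.0 |

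**Incomplete recording.** Take s = 95%, 400,000 infant-days, 40% exposed, an event probability of 1.8%, o0 = 2%, o1 = 6% and no drug effect. A logistic fit to expected counts gives an adjusted OR of 0.36, with a standard error of the log OR of about 0.03. One simulated data set of the same design gave 0.34. The factor 0.33 is therefore a close guide when capture is high but not perfect.

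**The extreme case.** If s = 1 and inotropes never occur on a non-event day, outcome and covariate coincide. The fit separates completely: a true OR of 2.0 is returned as 1.0, with a standard error of the log OR of about 25,800, so it is not estimable. If s = 1 but some non-event days carry inotropes, only the intercept and the inotrope coefficient diverge, and the ampicillin OR is still estimated.

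**Would model selection remove the covariate?** With s = 90% and the same background use o in both groups, the inotrope odds ratio is (0.9/0.1) × (1 − o)/o.

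- o = 10%: 9 × 9 = 81, log OR 4.4
- o = 2%: 9 × 49 = 441, log OR 6.1
- o = 0.1%: 9 × 999 = 8,991, log OR 9.1

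A predictor this strong survives a likelihood ratio test. The planned multicollinearity check compares covariates with each other, so it does not look for overlap with the outcome.

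**Could o0 and o1 differ?** Only the first diagnosis is an event. Later days on pressors are therefore non-event days with an inotrope, unless they are taken out of the comparison, which section 10.4.2 does not say. Section 2.1.1 presents ampicillin as treatment for sepsis, so circulatory support may well differ between exposed and unexposed days. The documents give neither the size nor the direction of any difference.

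**Leaving the covariate out.** Without inotropic support, the fitted OR equals the assumed OR (1.0 or 2.0) in every equal-background scenario run. This holds because no other confounding was built in.

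**The case against.** The strongest reply is that the protocol never says inotropic support is taken on the event day. Support recorded beforehand would be an ordinary severity adjuster, and covariate timing is often left to a statistical analysis plan, which is not at hand. The on-ampicillin column of Table 3 covers the whole exposure period, so it does not prove same-day coding. This stands as far as it goes: same-day coding is an inference. But the infant-day comparison and the absence of any prior-day clinical values in Table 3 point towards it, and the harmless reading has no data behind it in that table.

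Two points of wording also carry some weight. The covariate list is introduced as examples; the full model, however, is then defined by the variables listed. And inotropic support and pressors are not stated to be the same variable; they overlap, and the distortion weakens as the overlap shrinks.

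The calculation assumes no difference in severity between exposed and unexposed days. If sicker infants receive both ampicillin and inotropes, dropping the covariate leaves some confounding. That is a real cost of one of the two remedies.

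Three stronger readings are tempting and are not supported:

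- A reader might infer that this odds ratio is meaningless or that the fit must fail. It fails only if inotropes never occur on non-event days, and it is undistorted if o0 = o1.
- A reader might extend the point to cardiorespiratory arrest through same-day ventilation. The documents do not say whether ventilation began before or after the arrest.
- A reader might conclude that the chart review cannot apply the pressor criterion because Table 2 has no medication row. Its data come from the medical record (section 6.1.2.1), and a reviewer can apply the Table 4 definition when marking hypotension. That cohort also receives only summary statistics, so the regression does not concern it.

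**Conclusion.** The point holds for one of the 17 diagnoses. As written, section 10.4.2 adjusts this hypotension outcome for a treatment that overlaps its definition, and nothing in the section prevents that treatment from being coded on the event day.

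If it is so coded and capture is complete or nearly so, the ampicillin odds ratio is multiplied by about o0/o1. That can erase a true doubling (2% versus 4%), turn it into an apparent protection of 0.67 (2% versus 6%), or inflate it to 4.0 (4% versus 2%). These sizes rest on assumed rates and on treating inotropic support and pressors as largely the same drug use; the documents fix neither. The separate difference between the hypotension labels in Tables 2 and 3 and in Table 4 is an inconsistency to reconcile, and it does not show that the data are unusable.

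**What to change.** In section 10.4.2, do one of the following for the hypotension diagnosis:

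- exclude inotropic support from its model; or
- adjust only for support that began before the event day, and say so.

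The first option costs one sentence and some loss of severity adjustment for this outcome. The second retains part of that adjustment, but needs the timing of support before the event day, which Table 3 does not mark at present. Neither requires a change to the models for the other outcomes.

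In addition, give the event the same definition in Tables 2, 3 and 4, so that the variable extracted is the one the analysis uses. This is an edit to the tables.

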Although ampicillin is the most commonly administered medication in the NICU, its safety in the neonatal population is poorly described. Adverse events (AE) listed on the FDA label for ampicillin are not specific to the neonatal population. Ampicillin AEs are mostly due to sensitivity phenomena that are more common in people with a history of penicillin exposure. This is very uncommon in the neonatal population. In a recent study comparing clinical efficacy of ampicillin or penicillin in combination with gentamicin therapy for early onset sepsis in infants (including GA <26 weeks), both were well tolerated with no difference in AEs or laboratory abnormalities. However, the focus of this study was clinical effectiveness comparison, and not safety profiling [15]. Among the potential serious AEs in infants is the risk of ampicillin induced seizures [4]. As with other penicillin's, β -Lactam-induced neurotoxicity is of concern if cerebrospinal fluid concentrations of ampicillin are high. This has been reported in adult case reports, but the incidence of seizures in infants, treated with ampicillin, has not been evaluated [16, 17]. Another

known side-effect of ampicillin most commonly seen after repeated dosing is inhibition of the coagulation cascade. The prevalence of this AE in the neonatal population, which is at risk of coagulopathy, is unknown [18]. Overall, given the importance of safety and improved long term outcomes in the neonatal population, a more detailed description of the safety of this commonly used antibiotic is warranted.

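### The Pediatrix seizure odds ratio has no direct adjustment for condition at birth: Apgar score is listed for the PK dataset but not for the safety extraction or model

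*Protocol*

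**What the plan says.** Section 2.1.2 of the protocol names seizure as a safety concern: "Among the potential serious AEs in infants is the risk of ampicillin induced seizures". It adds that the incidence in treated infants has not been evaluated. Appendix Table 4 classes seizure as a serious diagnosis.

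Under section 10.4.2 a diagnosis "will be attributed to ampicillin if it was first made on a day that the infant was exposed to ampicillin". The Pediatrix analysis then uses logistic regression "controlling for clinical factors associated with poor outcome in infants such as mechanical ventilation, inotropic support", together with "demographic features including race, gender, gestational and postnatal age". The largest model is fixed and can only shrink: "The full model containing all clinically relevant variables listed above will be compared to scaled down models". The output is an exposed-day versus unexposed-day comparison: "Odds ratios and 95% confidence intervals derived from this model will be reported".

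Section 6.1.2.2 sets the extraction: "The following clinical and demographic variables will be included in addition to date of birth, gestation age, race, ethnicity, sex, and birth weight". Table 3 then adds diagnoses, laboratory values, cultures, days of ampicillin, mechanical ventilation, fraction of inspired oxygen and concomitant medications. Apgar score is in neither list. It does appear, subject to availability, among the PK database variables in section 6.1.1.

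**The concern.** Infants in poor condition at birth can have seizures in the first days of life for reasons unrelated to any drug. Those are also days on which ampicillin is likely to be given. If such infants are also more likely than their peers to be on ampicillin, condition at birth confounds the seizure comparison.

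Adjusting for gestational and postnatal age does not remove this, because the imbalance is among infants of the same age. Ventilation and inotropic support are in the model but are only partial proxies. A better covariate cannot enter later under the plan as written: the full model is limited to the listed variables, and the extraction does not collect one.

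At stake is a seizure odds ratio above 1 that comes partly or wholly from the infants' condition. Section 10.1.2 anticipates about 400,000 exposed and 300,000 unexposed infants. The interval around a biased estimate could therefore be narrow enough to look like a drug signal.

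**Working it through.** The protocol gives no seizure rate, effect size or power for this comparison, so it has no figure to reproduce. The check has two parts.

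**1. Variable lists side by side**

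| Item | PK dataset (6.1.1) | Pediatrix extraction (6.1.2.2, Table 3) | Full model (10.4.2) |
|---|---|---|---|
| Apgar score | listed, if available | absent | absent |
| Gestational age | yes | yes | yes |
| Postnatal age | yes | derivable from date of birth | yes |
| Mechanical ventilation | not listed | yes | yes |
| Inotropic support | not listed by name | not listed by name; concomitant medications are | yes |
| Base excess | not listed | yes, as a laboratory outcome | absent |

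Table 2, for the PPRU chart review, also lacks Apgar score, but that cohort is only summarised descriptively.

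**2. Size under no drug effect, within one early postnatal day**

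All inputs are assumptions:
- p = share of infants depressed at birth: 0.5-2%
- RR = seizure risk in them relative to others: 10-50
- e1 = share of depressed infants on ampicillin: 85-95%
- e0 = share of other infants on ampicillin: 60-69%. The only related figure in the protocol is 693 per 1000 discharged infants ever exposed (section 2.1.1), which is not a daily share.

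Relative seizure risk on exposed days: A = [p·e1·RR + (1−p)·e0] / [p·e1 + (1−p)·e0]

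Relative seizure risk on unexposed days: B = [p·(1−e1)·RR + (1−p)·(1−e0)] / [p·(1−e1) + (1−p)·(1−e0)]

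Apparent ratio = A/B. For a rare event this is close to the odds ratio.

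Worked example (p = 1%, RR = 20, e1 = 95%, e0 = 60%):
- A = (0.190 + 0.594) / (0.0095 + 0.594) = 0.784 / 0.6035 = 1.299
- B = (0.010 + 0.396) / (0.0005 + 0.396) = 0.406 / 0.3965 = 1.024
- A/B = 1.27

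Ends of the range:
- Lowest (p = 0.5%, RR = 10, 85% versus 69%): 1.055 / 1.022 = 1.03
- Highest (p = 2%, RR = 50, 95% versus 60%): 2.534 / 1.125 = 2.25

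Sensitivity to exposure in other infants, with p = 1% and RR = 20:

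| e1 | e0 | Apparent ratio |
|---|---|---|
| 95% | 60% | 1.27 |
| 95% | 85% | 1.14 |
| 95% | 90% | 1.10 |
| 95% | 95% | 1.00 |
| 85% | 90% | 0.92 |

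**How far ventilation adjustment helps.** This is a separate illustration by logistic regression on expected counts, with a true odds ratio of 1. It assumes 5% depressed, a 10-fold seizure risk, a base seizure risk of 0.001, 90% of depressed infants on ampicillin, and ventilation in 50% of depressed and 20% of other infants.

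| Other infants on ampicillin | Unadjusted OR | Adjusted for ventilation | Plus a perfect marker of depression |
|---|---|---|---|
| 50% | 1.63 | 1.61 | 1.00 |
| 70% | 1.36 | 1.35 | 1.00 |
| 85% | 1.13 | 1.13 | 1.00 |
| 90% | 1.00 | 1.00 | 1.00 |

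Under these inputs ventilation removes little of the bias. A stronger link between ventilation and depression at birth would let it remove more. Apgar score is not a perfect marker, so it would remove less than the last column shows.

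**The case against.** The strongest reply is that the exposure contrast is assumed. If early ampicillin is close to universal, depressed infants and their peers are exposed about equally and the bias within an age stratum vanishes. If peers are exposed more, it reverses. This stands: the protocol gives no exposure by day of life, so neither direction nor size can be read from it.

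The comparison population is also not fully settled. Section 10.4.2 introduces the comparison for infants exposed to ampicillin, while sections 4, 5.1.2 and 10.1.2 point to a wider population. Among ever-exposed infants only, an exposure share of 60-69% based on all NICU infants would not apply. This too limits what can be said about size.

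A third reply is that the covariate list is introduced by way of example, and that exact covariates are normally left to the SAP. This carries less weight. The next step ties the full model to the listed variables and allows only reduction, and Table 3 does not collect Apgar score.

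Fourth, ventilation, inotropic support and early base excess reflect an infant's condition. They are partial proxies, so saying that nothing in the plan bears on condition at birth would go too far. What is absent is a direct marker.

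A reader might also infer that the seizure result will be biased upward, or that seizure is the study's leading safety result. The documents support neither. The bias is conditional, and seizure is one of 17 listed diagnoses with no primary outcome named among them.

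**Conclusion.** The point holds as a conditional weakness that is cheap to reduce. The plan fixes a full model and an extraction without a direct marker of condition at birth, while listing Apgar score for its other objective. Seizure is the outcome for which this matters most clearly. No size has been worked out for other outcomes.

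Under the stated assumptions, the spurious ratio before ventilation adjustment is 1.03-2.25, with 1.27 in the worked example. The top value needs all four inputs at their extremes together. With equal or higher exposure in other infants the ratio is 1.00 or below. The case for changing the plan does not depend on where in that range the truth lies: the protocol gives no grounds for ruling out a material bias, and a large sample does not reduce it.

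**What to change.** 1. Add the 5-minute Apgar score to the Table 3 extraction and to the full model in section 10.4.2. That the database holds it is an assumption to confirm first. For seizure, retain it regardless of the likelihood ratio reduction, since a confounder should not be dropped on a fit criterion.
2. If the database does not hold it, state the limitation in the protocol and report a quantitative bias analysis for seizure, using the formula above with exposure by postnatal day taken from the data.
3. A seizure odds ratio restricted to postnatal day 4 onward, matching the early/late boundary in section 2.1.1, may be reported as a labelled sensitivity analysis only. From that age ampicillin may be given for suspected late-onset sepsis, which may itself cause seizures. The restriction may therefore exchange one confounder for another, and it leaves fewer events.

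The cost is one extracted variable and one retained model term. Some Apgar values will be missing, and some confounding will remain because Apgar is an imperfect marker. The day-of-exposure attribution rule would still count the same seizures as ampicillin events in the raw frequencies; only the odds ratio changes.

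### Covariates for the Pediatrix odds ratios are pruned by likelihood ratio tests, and the named set leaves out infection status and co-administered antimicrobials

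*Protocol*

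**What the plan says.** Protocol Section 10.4.2 plans multivariable logistic regressions in which the odds of a diagnosis or laboratory abnormality on an ampicillin day "will be compared to the odds of occurrence on a day the infant was not exposed to ampicillin". Adjustment is for "clinical factors associated with poor outcome in infants such as mechanical ventilation, inotropic support, and demographic features including race, gender, gestational and postnatal age". The model is then reduced: "The full model containing all clinically relevant variables listed above will be compared to scaled down models using likelihood ratio tests". No test level is given, and no covariate is kept in regardless of the tests. Among the models so compared, "the most parsimonious model that fits the data will be used for analysis". The section ends: "Odds ratios and 95% confidence intervals derived from this model will be reported".

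Infection status and other antimicrobials are not among the named variables. Section 2.1.1 gives infection as the drug's indication. Section 2.1.2 cites a study of "ampicillin or penicillin in combination with gentamicin therapy for early onset sepsis".

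Table 3 (Section 6.1.2.2) has rows for "Positive Blood/Urine/CSF Cultures", marked from day -3 to day +3 around ampicillin, and for "Concomitant medications", marked in the on-ampicillin column only. Mechanical ventilation is also marked in that column only.

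**The concern.** The purpose of this regression is to estimate the association of ampicillin with harm after controlling for other factors. A likelihood ratio test asks whether a covariate improves prediction of the outcome. It does not ask whether removing that covariate moves the ampicillin odds ratio. A variable strongly linked to exposure and moderately linked to a rare outcome can fail the test and still confound. Intervals computed from the selected model as if it had been fixed in advance also ignore the selection. With six named covariates and hundreds of thousands of infants, there is no overfitting for parsimony to cure in general, and for rare outcomes the rule is most likely to remove something that matters.

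The second part is confounding by indication. Ampicillin days are days on which infection is treated or suspected. Hypotension, thrombocytopenia, leukopenia, raised creatinine and seizure, all in Appendix Tables 4 and 5, can plausibly arise from infection or from another drug given with ampicillin. The Protocol describes no matching, restriction, active comparator, propensity score or within-infant conditioning, so the covariates carry the whole burden. At this sample size the intervals for common outcomes are narrow, and a modest bias could look like a firm safety signal.

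**Working it through.** The Protocol gives no power calculation, event rate or expected odds ratio for Objective #2, so there is no stated figure to reproduce. The checks below are illustrations. From the Protocol come the counts of 400,000 exposed and 300,000 unexposed infants (Section 10.1.2), early and late onset sepsis incidences of 1.2% to 2% and 14% to 36%, and an ampicillin exposure rate of 693 per 1000 (all Section 2.1.1). Everything else is assumed. Records are treated as independent, and per-infant figures stand in for per-day ones.

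**Pruning.** Assume a 5% test and a covariate with prevalence 20% and odds ratio 1.5.
- Share of events carrying it: 0.2 × 1.5 / (0.2 × 1.5 + 0.8) = 0.273.
- With 100 events, SE(log OR) ≈ √(1/27.3 + 1/72.7) = 0.224, and z = ln 1.5 / SE = 1.81. The chance of retention is about Φ(1.81 − 1.96) = 44%, so the covariate is dropped 56% of the time.
- With 500 events, SE = 0.100 and z = 4.04. Retention is 98%, so it is dropped 2% of the time.
- As shares of 700,000 infants, 100 and 500 events are 0.014% and 0.071%.

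A second version takes prevalence q = 10%, odds ratio 1.5, N = 700,000, outcome frequency p, and z = ln(OR) × √(N p(1−p) q(1−q)). Retention is 1.00 at p = 1%, 0.90 at 0.1%, 0.62 at 0.05% and 0.17 at 0.01%. Pruning therefore matters mainly for rare outcomes.

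**Omitted covariates.** For an omitted binary factor and a rare outcome, the observed odds ratio divided by the true one is [1 + p1(RR − 1)] / [1 + p0(RR − 1)], where p1 and p0 are its prevalences with and without ampicillin.

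| Omitted factor | p1 vs p0 | RR | Bias factor |
|---|---|---|---|
| Early sepsis at 2%, all among the exposed (0.02/0.693) | 2.9% vs 0 | 2 / 3 / 5 | 1.03 / 1.06 / 1.12 |
| Infection | 10% vs 2% | 5 | 1.40/1.08 = 1.30 |
| Infection | 20% vs 10% | 2 / 3 / 5 | 1.09 / 1.17 / 1.29 |
| Infection, ends of the late onset range | 36% vs 14% | 2 / 3 / 5 | 1.19 / 1.34 / 1.56 |
| Infection, imbalance reversed | 10% vs 20% | 2 / 3 / 5 | 0.92 / 0.86 / 0.78 |
| Co-antimicrobial | 90% vs 30% | 1.2 / 1.5 / 2 | 1.11 / 1.26 / 1.46 |
| Co-antimicrobial | 80% vs 5% | 1.5 / 2 | 1.37 / 1.71 |

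For comparison, the 95% interval runs from the estimate divided by a factor to the estimate times that factor. The factor is exp(1.96 × √(1/(400,000 p(1−p)) + 1/(300,000 p(1−p)))), which is 1.05 at p = 1% and 1.16 at p = 0.1%. Many of the biases in the table would fall outside such an interval.

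A simulated logistic regression on 700,000 records with a true ampicillin odds ratio of 1.00 and a strong assumed imbalance (from 15.3% vs 1.6% to 47.3% vs 7.5%) gave odds ratios of 1.12 to 1.74 without the infection indicator and 0.97 to 1.02 with it. This shows that the right covariate removes the bias. It says nothing about how large the bias is in these data.

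**The case against.** **The list is open.** The covariates are introduced by *such as*, and a full list is commonly left to the analysis plan. That stands in part: a reader might infer that the Protocol bars infection status from the model, and it does not firmly do so. The next step does, however, define the full model by the variables listed above it. The omission is therefore weaker ground than the pruning rule, which is stated outright.

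**Pruning rarely bites, and costs little where it does.** Retention is near certain for a 1% outcome. With 100 events, dropping a covariate with odds ratio 1.5 present on an assumed 30% vs 10% of days shifts the ampicillin odds ratio by 1.15/1.05 = 1.10. The interval factor with events split 57/43 is exp(1.96 × √(1/57 + 1/43)) = 1.49. That is fair for a single covariate. It does not make the rule useful, since it offers nothing in return and leaves the interval uncorrected for selection.

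**The data are not simply at hand.** A reader might infer from Table 3 that the missing covariates are already extracted. As laid out, it supplies concomitant medications only on ampicillin days, without naming antimicrobials, and cultures only within three days of ampicillin. The regression also needs unexposed days.

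**Gentamicin.** A reader might infer from Section 2.1.2 that the two drugs are usually combined in these units. The section describes one comparative study and gives no frequency, so the co-antimicrobial prevalences above have no source in the Protocol.

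**Different covariates for different outcomes** are not an error in themselves. The objection here is to choosing them by test.

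**Conclusion.** The pruning rule is unsuited to the stated aim and should go. On assumed inputs it drops a real covariate more than half the time at 100 events and hardly ever at 500, so the exposure lies in rare serious outcomes. The larger issue for the estimates is that the named set contains neither infection status nor co-administered antimicrobials and nothing else controls for indication.

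It would be tempting to say that the odds ratios are biased upward by a known amount. The documents do not support that. Upward is the likelier direction if infection is commoner on ampicillin days and raises the odds of the outcome, but a reversed imbalance gives factors of 0.78 to 0.92. The ranges of 1.03 to 1.56 for infection and about 1.1 to 1.7 for co-antimicrobials show what plausible inputs would do. They are not estimates for this database. The Synopsis and Section 5.1.2 give about 400,000 database infants in all, against 700,000 in Section 10.1.2; the argument is the same at either size.

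**What to change.** In Section 10.4.2, delete the likelihood ratio reduction and the parsimony sentence. Report odds ratios and intervals from one prespecified full model for each outcome. State an exception where a covariate overlaps the outcome: inotropic support should not adjust the model for hypotension requiring pressors (Appendix Table 4).

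Add to the named covariates:
- infection status measured at or before the start of exposure; cultures from days +1 to +3 are post-exposure and should not be used for adjustment;
- concomitant antimicrobials. Where one is almost always given with ampicillin, state that the odds ratio describes the combination.

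Extend the Table 3 extraction of cultures, concomitant medications and ventilation to unexposed days. Acknowledge residual confounding, because culture positivity misses suspected sepsis; the gap between 693 per 1000 exposed and 1.2% to 2% early onset sepsis suggests that much use is without proven infection.

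The cost is wording and code, a somewhat wider data pull from the same database, slightly wider intervals for rare outcomes and some collinearity, for which the section already plans an evaluation.
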